### **9.7.8 Analysis of pharmacokinetics**

Analysis of PK will be performed in the PK analysis set.

A frequency table will be provided for approaches to PK dosing, and if needed and data permits, subgroup analysis may be performed based on the subgroups defined in Section 9.7.1.

For the primary analysis, summary statistics (n, mean, SD, median, minimum, first quartile [Q1], third quartile [Q3], maximum, geometric mean, geometric SD, and coefficient of variation) will be displayed for PK measurement results.

If data permit, the difference in PK parameters of damoctocog alfa pegol and pre-treatment will be evaluated on a log scale.

Listings will be provided for all available PK measurements collected at baseline and during the study.

## 9.8 Quality control

### 9.8.1 Data quality

Before study start at the sites, all physicians will be sufficiently trained on the background and objectives of the study and on the ethical as well as regulatory obligations. Physicians will have the chance to discuss and develop a common understanding of the OS protocol and the eCRF.

A CRO will be selected and assigned for EDC system development, quality control, verification of the data collection, data analysis and data transfer to Bayer.

All observations will be recorded in a standardized eCRF. After data entry, missing or implausible data will be queried and the data will be validated. A check for multiple documented patients will be performed. Operational measures which positively impact data quality will be considered as required. If such measures are used, the documentation can be made available upon request (see [Table 6](#)).

Detailed information on checks for completeness, accuracy, plausibility and validity are given in the DMP. The DMP will specify measures for handling of missing data and permissible clarifications. The DMP is available upon request (see [Table 6](#)).

Medical review of the data will be performed according to the Medical Review Plan (MRP). The purpose of the medical review is to verify the data from a medical perspective for plausibility, consistency, and completeness and to identify potential issues that could affect the robustness of the collected study data or the progress of the study. Detailed information on the Medical Review will be described in the MRP, which is available upon request (see [Table 6](#)).

National and international data protection laws as well as regulations on OS will be followed. Electronic records used for capturing patient data (eCRF) will be validated according to 21 Code of Federal Regulations (CFR) Part 11 (US Food and Drug Administration [FDA]) [30]. 21 CFR Part 11 regulations describe the criteria to consider electronic records including e-signatures to be reliable and generally equivalent to paper records and handwritten signatures. They mandate access controls to ensure that only authorized individuals can use the system, additionally a computer-generated audit trail has to be in place to record the date and time of any actions to create, modify, or delete electronic records. The documentation is available upon request (see [Table 6](#)).

### 9.8.2 Quality review

Quality review will be performed in 2 steps: in the first step the site's training status will be assessed via standardized telephone interviews. In the second step source data verification will be conducted. The purpose is to review the documented data for completeness and plausibility, adherence to the OS protocol and verification with source documents.

Detailed measures for quality reviews will be described in the Quality Review Plan, which is available upon request (see [Table 6](#)).

### **9.8.3 Storage of records and archiving**

Bayer will ensure that all relevant documents for this study will be stored after the end or discontinuation of the study for at least 25 years. Any data, as well as programs from statistical programming performed to generate results, will be stored within the programming system for at least 25 years. Other instructions for storage of medical records will remain unaffected.

The physicians participating in the study are required to archive documents at their sites according to local requirements, considering possible audits and inspections from the study initiator and funder and/or local authorities. It is recommended to store documents for a retention period of at least 25 years at the study sites.

### **9.8.4 Certification/qualification of external parties**

Not applicable.

## **9.9 Limitations of the research methods**

In general, because of the non-interventional study design and limitations inherent to observational studies, findings generated from this study are subject to bias, such as information bias, selection bias, limitations to availability of historical medical data, and differences in treatment or reporting owing to local guidelines.

The sample size is not large enough to observe extremely rare AEs. It may include limited availability of treatment data and underreporting of safety outcomes if a patient leaves the study and/or is not possible to be followed-up adequately (e.g., withdrawal of consent or lost to follow-up). The bleeding event, treatment pattern, PROs, and the drug utility data collected in this study may suffer from bias due to measured and unmeasured confounders, selection bias, as well as reporting bias. Additionally, both drug utility and adherence to treatment is prone to be biased by adherence to documentation. Finally, it is acknowledged that channelling bias (confounding by indication) can be present in observational studies despite use of more advanced study designs and analytical methods. Because confounders or risk factors are specific for each outcome, adjusting for confounding for each outcome would require complete information of measured and unmeasured risk factors for each outcome associated with exposure to damoctocog alfa pegol.

The diversity of the data sources may add complexity as the implementation of standardized bleed/infusion diaries may be difficult as patients may continue to use their own diaries (paper, electronic, or software). In addition, the information may only be available by means of the physician documents.

### **9.10 Other aspects**

Not applicable.

## **10. Protection of human subjects**

### **10.1 Ethical conduct of the study**

This study is an OS where damoctocog alfa pegol is prescribed in the customary manner in accordance with the terms of the marketing authorization. There is no assignment of a patient to a particular therapeutic strategy. The treatment decision falls within current practice and the

prescription of the medicine is clearly separated from the decision to include the patient in the study. No additional diagnostic or monitoring process is required for participation or during the study. Epidemiological methods will be used for the analysis of the collected data.

## **10.2 Regulatory authority approvals/authorizations**

The study will be carried out within an approved indication in accordance with guidelines and regulations of EMA, FDA, and applicable local law(s) and regulation(s) (e.g., European Union [EU] Regulation No 520/2012 [31]). Recommendations given by other organizations will be followed as well (e.g., European Federation of Pharmaceutical Industries and Associations [EFPIA] [32], European Network of Centers in Pharmacoepidemiology and Pharmacovigilance [ENCePP] [33]).

In addition, the guidelines on Good Pharmacovigilance Practices (GVP module VI [34] and since the study qualifies as a Post-Authorization Safety Study (PASS), GVP module VIII [35],[36]) will be followed.

## **10.3 Independent ethics committee (IEC) or institutional review board (IRB)**

In all countries where reference to an IEC/IRB is required, documented approval from appropriate IECs/IRBs will be obtained for all participating sites prior to study start. When necessary, an extension, amendment or renewal of the IEC/IRB approval must be obtained and also forwarded to the study initiator and funder. The IEC/IRB must supply to the study initiator and funder, upon request, a list of the IEC/IRB members involved in the vote and a statement to confirm that the IEC/IRB is organized and operates according to applicable laws and regulations.

## **10.4 Patient information and consent**

Before documentation of any data, informed consent is obtained by the patient/legal representative in writing. For patients under legal age at the time of enrollment, signed assent by the patient and parental/legal guardian signed informed consent will be obtained. In countries where required by law or regulation, the physician must have the IEC/IRB written approval/favorable opinion of the written informed consent form and any other written information to be provided to patients prior to the beginning of the observation.

## **10.5 Patient insurance**

In this observational study, data on routine treatment of patients in daily practice are documented and analyzed with the help of epidemiological methods. Treatment including diagnosis and monitoring of therapy follows exclusively routine daily practice. Current medical daily practice is observed, and for the patient no risks beyond regular therapy exist – there is no additional hazard arising from study participation. As no study-related risks exist, there is no need to protect the patient additionally with patient insurance. The general regulations of medical law and the professional indemnity insurance of the physicians and, respectively, the institutions involved provide sufficient protection for both patient and physician.

No study treatment will be provided to patients. Thus, product insurance is covered by the existing product liability.

## 10.6 Confidentiality

Bayer as well as all physicians ensure adherence to applicable data privacy protection regulation. Data are transferred in encoded form only. The entire documentation made available to Bayer does not contain any data which, on its own account or in conjunction with other freely available data, can be used to re-identify natural persons. The physicians are obligated to ensure that no documents contain such data.

All records identifying the patient will be kept confidential and will not be made publicly available. Patient names will not be supplied to Bayer AG. If the patient name appears on any document, it must be obliterated before a copy of the document is supplied to Bayer AG. Study findings stored on a computer will be stored in accordance with local data protection laws.

The physician will maintain a list to enable patients' records to be identified in case of queries. In case of a report of an SAE, the responsible pharmacovigilance person may ask for additional clarification. In that case, the company is not allowed to directly contact the patient. All additional information will be provided by the physician.

## 11. Management and reporting of adverse events/adverse reactions

### 11.1 Definitions

An Adverse Event (AE) is any untoward medical occurrence in a patient administered a medicinal product and which does not necessarily have a causal relationship with this treatment. An AE can therefore be any unfavorable and unintended sign (e.g., an abnormal laboratory finding), symptom, or disease temporally associated with the use of a medicinal product, whether or not considered related to this medicinal product [37].

The term also covers laboratory findings or results of other diagnostic procedures that are considered to be clinically relevant (e.g., that require unscheduled diagnostic procedures or treatments or result in withdrawal from the study).

The AE may be:

- A new illness.
- Worsening of a sign or symptom of the condition under treatment or of a concomitant illness.
- An effect of the study treatment.
- An effect of a concomitant medication or treatment.
- Off label use , occupational exposure, lack of drug effect, medication error, overdose, drug abuse, drug misuse or drug dependency itself, as well as any resulting event.

---

 According to GVP Module VI, off label use "relates to situations where the medicinal product is intentionally used for a medical purpose not in accordance with the authorized product information". Off label use *per se* is an AE, even if no AR is reported, therefore it needs to be ensured that all relevant variables to identify such potential incidents are collected (e.g., indication).

- An effect related to pre-existing condition improved (unexpected therapeutic benefits are observed).
- Product exposure via mother/father (exposure during conception, pregnancy, childbirth, and breastfeeding).

As mentioned above no causal relationship with a product is implied by the use of the term “adverse event”.

An Adverse Reaction (AR) is defined as a response to a medicinal product which is noxious and unintended. An AR is any AE judged as having a reasonable suspected causal relationship to damoctocog alfa pegol.

Causal relationship: The assessment of the causal relationship between an AE and the administration of treatment is a clinical decision based on all available information at the time of the completion of the eCRF. The assessment is based on the question whether there was a “reasonable causal relationship” to the study treatment in question. Possible answers are “yes” or “no”.

An assessment of "no" would include:

- The existence of a clear alternative explanation (e.g., mechanical bleeding at surgical site).
- Non-plausibility (e.g., the patient is struck by an automobile when there is no indication that the product caused disorientation that may have caused the event; cancer developing a few days after the first treatment administration).

An assessment of “yes” indicates that there is a reasonable suspicion that the AE is associated with the use of the study treatment. Factors to be considered in assessing the relationship of the AE to study treatment include:

- The temporal sequence from product administration: The event should occur after the product is given. The length of time from product exposure to event should be evaluated in the clinical context of the event.
- Recovery on product discontinuation (de-challenge), recurrence on product re-introduction (re-challenge): Patient’s response after de-challenge or patient’s response after re-challenge should be considered in the view of the usual clinical course of the event in question.
- Underlying, concomitant, intercurrent diseases: Each event should be evaluated in the context of the natural history and course of the disease being treated and any other disease the patient may have.
- Concomitant medication or treatment: The other products the patient is taking or the treatment the patient receives should be examined to determine whether any of them may be suspected to cause the event in question.
- The pharmacology and PK of the study treatment: The PK properties (absorption, distribution, metabolism and excretion) of the study treatment, coupled with the individual patient’s pharmacodynamics should be considered.

An AE or AR is serious (SAE) if it:

- Results in death.
- Is life-threatening.

- Requires in-patient hospitalization or prolongation of existing hospitalization (see exceptions below).
- Results in persistent or significant disability or incapacity.
- Is a congenital anomaly or birth defect.
- Is medically important.

Death is usually the outcome of an underlying clinical event that causes it. Hence, it is the cause of death that should be regarded as the SAE. The 1 exception to this rule is “sudden death” where no cause has been established. In this instance, “sudden death” should be regarded as the AE and “fatal” as its reason for being “serious”.

Life-threatening: The term “life-threatening” in the definition of “serious” refers to an AE in which the subject was at risk of death at the time of the event. It does not refer to an AE which hypothetically might have caused death if it were more severe.

Hospitalization: Any AE leading to hospitalization or prolongation of hospitalization will be considered as serious, unless the admission was:

- Planned before patient’s inclusion in the study (i.e., elective or scheduled surgery); or
- Ambulant (shorter than 12 hours); or
- Part of the normal treatment or monitoring of the studied disease (i.e., not due to a worsening of the disease).

However it should be noted that invasive treatment during any hospitalization may fulfill the criteria of “medically important” and as such may be reportable as an SAE dependent on clinical judgment. In addition, where local regulatory authorities specifically require a more stringent definition, the local regulation takes precedent.

Disability means a substantial disruption of a patient’s ability to conduct normal life functions.

Congenital anomaly (birth defect), i.e., any congenital anomaly observed in an infant, or later in a child, should be regarded as an SAE when:

- The mother had been exposed to a medicinal product at any stage during conception or pregnancy or during delivery.
- The father was exposed to a medicinal product prior to conception.

Other medically important serious event: any AEs may be considered serious as it may jeopardize the patient and may require intervention to prevent another serious condition. Medically important events either refer to or might be indicative of a serious disease state. Such reports warrant special attention because of their possible association with serious disease state and may lead to more decisive action than reports on other terms.

## 11.2 Collection

It should be documented in the eCRF whether the patient is participating in a registry or other program where reporting of AEs to a third party may occur in addition to the reporting requirements for this study.

Starting with the first administration of damoctocog alfa pegol after enrollment into the study, all non-serious AEs must be documented on the AE Report Form or in the eCRF/EDC system and forwarded to the Marketing Authorization Holder (MAH) within 7 calendar days (for EU countries or if required by local regulations of participating country) or 60 days (for countries outside the EU) of awareness. All SAEs must be documented and forwarded immediately (within 1 business day of awareness). For each AE, the physician must assess and document the seriousness, duration, relationship to product, action taken and outcome of the event.

If a pregnancy in the female partner of a male patient or in a female patient occurs during the study, although it is not an SAE itself, it should be documented and forwarded to the MAH within the same time limits as an SAE. The result of a pregnancy will be followed-up according to applicable Bayer standard operating procedures. Any data on abnormal findings concerning either the mother or the baby will be collected as AEs.

The documentation of any AE/SAE ends at the latest 30 days after the completion of the observation period of the patient: i.e., any AE/SAE - regardless of the relationship and the seriousness - occurring up to 30 days after the last dose of damoctocog alfa pegol within the patient's observation period has to be documented and forwarded to the MAH within the given timelines.

As long as the patient has not received any damoctocog alfa pegol within the frame of the study AEs/SAEs do not need to be documented as such in this OS. However, they are part of the patient's medical history.

For any serious product-related AE occurring after study end, the standard procedures that are in place for spontaneous reporting have to be followed.

### **11.3 Management and reporting**

#### Non-serious AEs

The outcome of all reported AEs will be followed-up and documented. Where required, physicians might be contacted directly by the responsible study staff to provide further information.

#### Non-serious ARs

All non-serious ARs occurring under treatment with damoctocog alfa pegol that qualify for expedited reporting will be submitted to the relevant authorities according to EU pharmacovigilance legislation (Regulation [EU] No 1235/2010 and Directive 2010/84/EU, Module VI [34]) and according to national regulations by the MAH; however, all physicians must obey local legal requirements.

For non-serious ARs occurring under non-Bayer products the physician has to account for and comply with the reporting system of the product's MAH within the frame of local laws and regulations as well as other locally applicable laws and regulations.

#### Serious AEs

Any SAE or pregnancy entered into the eCRF/EDC system will be forwarded immediately (within 1 business day of awareness) to the pharmacovigilance country person responsible for SAE processing. The outcome of all reported SAEs (resolution, death, etc.) will be followed-up and documented. Where required, physicians might be contacted directly by the pharmacovigilance country person in charge to provide further information.

Submission to the relevant authorities according to national regulations will be performed by the MAH for SAEs related to damoctocog alfa pegol treatment; however, all physicians must obey local legal requirements.

For any serious drug-related AE occurring after study end, the standard procedures that are in place for spontaneous reporting have to be followed.

For SAEs that occurred while administering non-Bayer products the physician has to account for and comply with the reporting system of the product's MAH within the frame of local laws and regulations as well as other locally applicable laws and regulations.

Submission of SAEs related to non-Bayer products to the relevant authorities according to national regulations will be performed by the product's MAH.

#### AEs of special interest:

The following AEs of special interest are reported (if done in routine clinical practice):

- Hypersensitivity reactions including skin-related and systemic reactions, such as anaphylactic reactions (seriousness should be a case-by-case decision).
- Inhibitor development: inhibitors need to be assessed as mandatory serious and reported to Bayer AG within 24 hours of awareness.
- Loss of drug effect (immune-response to PEG, anti-drug antibodies, etc.).
- Renal impairment.,
- Neurocognitive disorders.,

The reporting physician will be asked to complete additional questionnaires when any of the above AEs of special interest are reported

Any bleeding event occurring during the study will not be documented as an AE, as long as it is not considered to have a "causal relationship" to the product. The events are captured in the assessment of effectiveness. However, if the bleed requires hospitalization, it must be reported as an SAE.

The physician will be asked to document in the eCRF whether the clinical site participates in any registries whereby AEs could be reported to both the registry and the HEM-POWR study.

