**Table 3: Tabulated overview on data collected during the study**

	Enrollment/ Initial visit	Follow up visit (including end of observation)
Eligibility Assessment (see 9.2.2)	X	
Date	X	X
Demographic data (see 9.3.3)	X	
General medical/surgical history (see 9.3.5)	X	
Disease history (see 9.3.4)	X	
Bleed history (see 9.3.1)	X	
Prior FVIII treatment history (see 9.3.4)	X	
Damoctocog alfa pegol history (if any, see 9.3.7)	X	
Current prescribed damoctocog alfa pegol regimen (see 9.3.7)	X	X
Damoctocog alfa pegol dose/regimen changes, treatment switches (see 9.3.7)		X (Continuous collection)
Patient-Reported Data (Hemo-SAT A, Hemo-QoL-A, Hemo-QoL Short Form, WPAI [+ CIQ: HS]; see 9.3.10)	X	X (Month 12, 24, 36)

	Enrollment/ Initial visit	Follow up visit (including end of observation)
Physical examination (weight, height, vital signs) 	X	X
Joint Health (HJHS)	X	X
Ultrasound data 	X	X
Affected joints	X	X
Damoctocog alfa pegol Pharmacokinetic analysis  (see 9.3.7)	X	X
Concomitant medication (see 9.3.6)	X	X
Adverse events (includes systematically collected AEs and AEs of special interest (see 11)) 	X (Continuous collection)	
Inhibitor 	X	X
Patient infusion diary		X (Continuous collection)
Physician recorded bleeds 		X (Continuous collection)
Physician recorded surgeries		X (Continuous collection)
Reason for end of observation (see 9.3.11)		X (once, at occurrence)

 Routine examinations only, if available.

 PK analysis is at physician's discretion. PK testing (and the frequency of testing per the table) is part of the routine use of the product.

 Adverse events (up to 30 days after the last treatment with damoctocog alfa pegol in study period).

 Serious, life-threatening bleeds and surgery bleeds to be recorded by the physician. Physician to ask patient at each visit regarding bleeds.

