### **9.3.8 Inhibitor measurement**

Data documented by the physician, if collected, include:

- Date of measurement.
- Inhibitor test result (negative/positive).
- Titer of inhibitor (Bethesda units).

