### **9.3.9 Exploratory Assessment (PEG measurement)**

Data on PEG measurements will be recorded if it is part of the routine practice.

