### **9.7.7 Analysis of adverse events**

The analysis described in this section will be performed on incident treatment-emergent adverse events (TEAEs) on the SAF.

An overview table displaying all TEAEs will be presented. This overview table will provide a summary on patient level:

- Any event (AE of special interest, AE, SAE, and AR).
- Maximum intensity of events.
- Events with outcome of death.
- Events leading to change of treatment regimen of study treatment.
- Events leading to discontinuation of study treatment.
- Events related to inhibitor development.

AEs will be coded using the latest version of MedDRA. A summary of TEAEs will be presented by primary System Organ Class (SOC) and Preferred Term (PT). AEs will primarily be classified by MedDRA PT. Aggregate incidences at the SOC level will be presented.

Each of the AEs of special interest will be described separately. Event rates and 95% CIs will be reported as both incidence risks and exposure-adjusted incidence rates.

Additionally, a detailed listing will be provided for AEs related to the development of an inhibitor or positive inhibitor measurements, including information on history of inhibitors.

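### Section 11.3 makes special-interest AE reporting conditional on routine practice, against Section 11.2 and Table 3, and the protocol lists no renal or cognitive assessment data to show who was examined

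*Protocol*

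**What the plan says.** **Reporting rule.** Section 11.3, under the special-interest heading, opens with "The following AEs of special interest are reported (if done in routine clinical practice)" and then lists five event types, among them renal impairment and neurocognitive disorders. Section 11.2 carries no such condition: "all non-serious AEs must be documented on the AE Report Form or in the eCRF/EDC system", and SAEs must be forwarded within one business day. The AE row of Table 3 names special-interest events, marks them as continuously collected and carries only footnote 3 (the 30-day window). Footnote 1, which restricts an item to routine examinations, is attached to physical examination, ultrasound, PK and inhibitor, but not to AEs.

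**What is recorded.** Section 10.1 states: "No additional diagnostic or monitoring process is required for participation or during the study". Some results are nevertheless captured when they exist. Section 9.3.8 records "Inhibitor test result (negative/positive)" with date and titer, Section 9.3.7 records PK parameters, and Section 9.3.9 says "Data on PEG measurements will be recorded if it is part of the routine practice". The general clinical row of Table 3 is "Physical examination (weight, height, vital signs)". Neither Table 3 nor Section 9.3 lists a renal-function value or a cognitive assessment.

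**What is analysed.** For each special-interest event, Section 9.7.7 plans: "Event rates and 95% CIs will be reported as both incidence risks and exposure-adjusted incidence rates".

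**The concern.** Long-term safety of a PEGylated product is a stated aim (Sections 7.2 and 8.2), and renal impairment and neurocognitive disorders are two of the events the study was set up to watch. Two features weaken what it can say about them.

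First, read literally, the condition in Section 11.3 gives the events of greatest interest a weaker reporting duty than an ordinary AE. An event is not something that is done or not done in routine practice; a test is. Sites in more than 20 countries may read the sentence differently.

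Second, a falling renal function without symptoms, or a slight cognitive change, is found mainly by someone looking. If the data do not show who was examined, a low rate could mean few events or few examinations, and a reader of the final report could not tell which.

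**Working it through.** **1. The reporting rule, side by side**

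| Place in protocol | Duty for special-interest AEs |
|---|---|
| Section 11.2 | All AEs and SAEs documented; no routine-practice condition |
| Table 3, AE row | Continuous collection; footnote 3 only |
| Sections 9.1.2 and 9.3.2 | Endpoint variables (occurrence, duration, treatment, severity, outcome); no condition |
| Section 11.3 | Reported if done in routine practice |

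Three places are unconditional and one is conditional. Section 11.3 itself treats inhibitors as mandatory serious events, so its condition cannot sensibly apply to everything in its own list.

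**2. The data listed, by event type**

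| Event | Baseline history | Routine test result listed, including normal results |
|---|---|---|
| Inhibitor development | Yes (9.3.4) | Yes (9.3.8) |
| Renal impairment | Yes (9.3.5) | No |
| Neurocognitive disorders | Yes (9.3.5) | No |

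For inhibitors, the number of patients tested can be counted because negative results are recorded. For the other two it cannot be counted from the listed variables. The renal and neurocognitive questionnaires (Section 11.3, Annex 5) are completed only after an event has been reported, so they add nothing for patients without a reported event.

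**3. The protocol's own detection figure**

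Inputs: n = 200, true risk 2.0%, at least 3 patients with events (Section 9.5, Table 5).

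P(X ≥ 3) = 1 − Σ(k = 0 to 2) C(200, k) p^k (1 − p)^(200 − k)

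With p = 0.02: 1 − (0.01759 + 0.07179 + 0.14577) = 0.76485, which reproduces the stated 76.5%. The calculation counts every true event as observed.

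**4. The same figure under partial ascertainment**

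Let s be the share of true events that routine care brings to light. **The documents give no value for s; the values below are assumptions.** The observed risk is 0.02 × s, and the formula in step 3 is applied to it.

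| s | Observed risk | Expected patients (200 × risk) | P(at least 3) |
|---|---|---|---|
| 1.00 | 2.0% | 4.0 | 76.5% |
| 0.75 | 1.5% | 3.0 | 57.9% |
| 0.50 | 1.0% | 2.0 | 32.3% |
| 0.25 | 0.5% | 1.0 | 8.0% |

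The four probabilities can also be read from the last row of Table 5, under 2.0%, 1.5%, 1.0% and 0.5%.

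**5. The stated limitations**

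Section 9.9 names information bias, reporting bias, reporting differences arising from local guidelines, and underreporting when a patient leaves or cannot be followed. It does not say that detection of some special-interest events depends on whether a test was done.

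**The case against.** The strongest reply is that these events are AEs, and Section 11.2 already requires all AEs to be documented. The AE definition in Section 11.1 is broad: "The term also covers laboratory findings or results of other diagnostic procedures that are considered to be clinically relevant". A diagnosed renal or cognitive disorder, a symptomatic one, or an abnormal result judged relevant must therefore be reported whatever the site's testing habits. This stands. A reader might infer that the planned rates measure testing frequency instead of harm, or that the two conditions are recorded only as baseline co-morbidities. The documents support neither reading: Section 9.3.2 makes the on-study events endpoint variables, and recognised events fall under Section 11.2.

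A second reply is that a non-interventional study cannot mandate tests. That is right, and the lack of mandated tests is not the point. Recording a result already in the chart adds no procedure, and the protocol does exactly that for inhibitors.

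Third, the figures in step 4 rest on s. It is tempting to equate s with the share of patients tested. That would require that no event is noticed without a formal test and that testing is unrelated to risk. If physicians test those with symptoms or risk factors, s exceeds the share tested and the loss is smaller. For the same reason, a rate among tested patients is not a corrected rate; it may be too high.

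Fourth, Table 3 is described as typical information, each assessment is to be entered in the eCRF, and neither the CRF nor the questionnaire content is shown. So one can say only that the protocol text does not list these items, not that the database lacks them. The contradiction over reporting remains either way.

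**Conclusion.** The point holds in two parts. The reporting rule in Section 11.3 contradicts Section 11.2 and Table 3; this is a matter of text and needs no assumption. On the variables the protocol lists, patients never assessed for renal or cognitive change cannot be separated from patients with normal findings, so the risks and rates of Section 9.7.7 are likely lower bounds for silent or subtle events. This second part assumes that the CRF, which is not shown, holds no further renal or cognitive fields.

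The size cannot be determined from the documents. Over the assumed range of 75% down to 25% of events ascertained, the 76.5% detection chance becomes 57.9% down to 8.0%. This shows how sensitive the Table 5 argument is to incomplete ascertainment; it does not estimate what will happen. Inhibitor development is outside this second part, because its negative tests are recorded. The change is worth making because it is cheap and the events concern a stated safety objective.

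**What to change.** 1. **Section 11.3:** state that special-interest AEs are reported whenever they come to the physician's attention, and that only the underlying diagnostic tests are limited to routine practice. This brings it into line with Section 11.2 and Table 3.
2. **Table 3 and Section 9.3:** add serum creatinine/eGFR (date, value) and whether a cognitive assessment was done (date, result), both under footnote 1. If the CRF already holds these fields, it is enough to list them.
3. **Section 9.7.7 or the SAP:** beside the safety-set rates, give the number and person-years of patients with at least one on-study assessment, separately for renal and cognitive. Add a baseline-to-worst shift table for renal function only; cognitive instruments may differ between sites and their results cannot be pooled that way. Label any rate among tested patients as descriptive, because testing may be selected by indication.
4. **Section 9.9:** name test-dependent ascertainment as a limitation.

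Cost: some rewording, a few optional fields with slightly more data entry, and one more table. No test or visit is added.
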